3.3 Discontinuation from Study Treatment

Patients will be discontinued from study treatment for any of the following reasons:

- Disease progression.
- Irreversible or intolerable toxicity or abnormal laboratory values.
- Patient requests to withdraw from the study and discontinue treatment.
- Inability of the patient to comply with study requirements.
- Conditions requiring therapeutic intervention not permitted by the protocol.
- Intercurrent illness (this will be at the investigator's discretion).
- Non-compliance or lost to follow-up.

After discontinuation from protocol treatment, patients must be followed for AEs for 30 calendar days after their last dose of study drug. All new AEs occurring during this period must be reported and followed until resolution, unless, in the opinion of the investigator, these values are not likely to improve because of the underlying disease. In this case, the investigator must record his or her reasoning for this decision in the patients' medical records and as a comment on the electronic Case Report Form (eCRF).

All patients who have Grade 3 or 4 laboratory abnormalities (Common Terminology Criteria for Adverse Events [CTCAE] v4.0 (<http://evs.nci.nih.gov/ftp1/CTCAE/CTCAE>) at the time of discontinuation must be followed until the laboratory values have returned to Grade 1 or 2, unless it is, in the opinion of the investigator, not likely that these values are to improve. In this case, the investigator must record his or her reasoning for making this decision in the patients' medical records and as a comment on the CRF.

3.4 Pregnancy

Patients, even if surgically sterilized, must:

CONFIDENTIAL

STUDY DRUG(S): EVEROLIMUS
FINAL PROTOCOL DATE: 19 JUNE 2014

SCRI INNOVATIONS STUDY NUMBER: BRE 212
VERSION 1.0

- Agree to practice effective barrier contraception during the entire study treatment period and for 6 months after the last dose of study drug, or
- Agree to completely abstain from heterosexual intercourse.

During the course of the study, all female patients of childbearing potential (the definitions of “women of childbearing potential” are listed in Appendix C) must contact the treating investigator immediately if they suspect that they may be pregnant (a missed or late menstrual period should be reported to the treating investigator), despite following the precautions listed above.

If an investigator suspects that a patient may be pregnant prior to administration of study drug(s), the study drug(s) must be withheld until the result of the pregnancy test is confirmed. If a pregnancy is confirmed, the patient must not receive any study drug(s), and must be discontinued from the study.

If an investigator suspects that a patient may be pregnant after the patient has been receiving study drug(s), the study drug(s) must immediately be withheld until the result of the pregnancy test is confirmed. If a pregnancy is confirmed, the study drug(s) must be immediately and permanently stopped, the patient must be discontinued from the study, and the investigator must notify the Sarah Cannon Research Institute (SCRI) study chair as soon as possible. If a patient becomes pregnant while enrolled in the study, a Pregnancy Form (a paper report form) should be completed and faxed to SCRI Safety Department. For more details regarding handling and reporting of pregnancies that occur during treatment, see Section 11.2.

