11.4 Protocol-Defined Events of Special Interest

The following are events of special interest, and will need to be reported expeditiously (see Section 11.2). These events include the following:

Pregnancy, Abortion, Birth Defects/Congenital Anomalies:

If a patient becomes pregnant while enrolled in the study, a Pregnancy Form (a paper report form) should be completed and faxed to SCRI Innovations Safety Department. SCRI Innovations Safety Department should be notified expeditiously, irrespective of whether or not it meets the criteria for expedited reporting. Abortions (spontaneous, accidental, or therapeutic) must also be reported to SCRI Innovations Safety Department.

Congenital anomalies/birth defects always meet SAE criteria, and should therefore be expeditiously reported as an SAE, using the previously described process for SAE reporting. A Pregnancy Form should also have been previously completed, and will need to be updated to reflect the outcome of the pregnancy.

Sexually active males must use a condom during intercourse while taking the drug and for 8 weeks after stopping treatment and should not father a child in this period.

A condom is required to be used also by vasectomized men in order to prevent delivery of the drug via seminal fluid.

Female partners of male patients must also be advised to use one of the following contraception methods: Use of (1) oral, injected, implanted or other hormonal methods of contraception, or (2) intrauterine device (IUD) or intrauterine system (IUS), or (3) prior male/female sterilization.

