Appendix C: Guidelines for Female Patients of Childbearing Potential and Fertile Male Patients

Acceptable Contraception Methods:

Women of childbearing potential, defined as all women physiologically capable of becoming pregnant, must use highly effective contraception during the study and for 8 weeks after stopping treatment.

Highly effective contraception is defined as either:

True Abstinence When this is in line with the preferred and usual lifestyle of the subject. Periodic abstinence (e.g., calendar, ovulation, symptothermal, post-ovulation methods) and withdrawal are not acceptable methods of contraception.

Sterilization When a woman of childbearing potential has had surgical bilateral oophorectomy (with or without hysterectomy) or tubal ligation at least six weeks prior to study entry. In case of oophorectomy alone, only when the reproductive status of the woman has been confirmed by follow up hormone level assessment.

Male Partner Sterilization When the appropriate post-vasectomy documentation of the absence of sperm in the ejaculate.

Use of a combination of any two of the following (one from a + one from b):

- a) Placement of an intrauterine device (IUD) or intrauterine system (IUS).
- b) Barrier methods of contraception: Condom or Occlusive cap (diaphragm or cervical/vault caps) with spermicidal foam/gel/film/cream/vaginal suppository.

Fertile male patients, defined as all males physiologically capable of conceiving offspring, with female partners of child-bearing potential must use condoms plus spermicidal agent during the study treatment period and for 8 weeks after the last dose of study drug, and should not father a child during this period.

Male patients must also refrain from donating sperm during their participation in the study.

The following are acceptable forms of barrier contraception:

- Latex condom, diaphragm or cervical/vault cap when used with spermicidal foam/gel/film/cream/suppository

Unacceptable Contraception Methods: for women of childbearing potential include:

- IUD progesterone T
- Female condom

CONFIDENTIAL

STUDY DRUG(S): EVEROLIMUS
FINAL PROTOCOL DATE: 19 JUNE 2014

SCRI INNOVATIONS STUDY NUMBER: BRE 212
VERSION 1.0

- Natural family planning (rhythm method) or breastfeeding
- Fertility awareness
- Withdrawal
- Cervical shield

Pregnancies

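### Contraception after treatment is required for 6 months in Section 3.4 but 8 weeks in Appendix C, the accepted methods also differ, and nothing says which rule prevails

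*Protocol*

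**What the plan says.** **Protocol Section 3.4 (Pregnancy).** The requirement opens with "Patients, even if surgically sterilized, must" and gives two alternatives: "Agree to practice effective barrier contraception during the entire study treatment period and for 6 months after the last dose of study drug, or" and "Agree to completely abstain from heterosexual intercourse". The 6-month period belongs to the barrier option; the abstinence option states no period of its own.

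**Protocol Appendix C.** Women of childbearing potential "must use highly effective contraception during the study and for 8 weeks after stopping treatment". Four routes qualify as highly effective:
- true abstinence that fits the patient's usual way of life;
- sterilization, meaning "surgical bilateral oophorectomy (with or without hysterectomy) or tubal ligation at least six weeks prior to study entry";
- a sterilized male partner;
- an intrauterine device or system (IUD/IUS) together with a barrier method.

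Fertile men whose partners could conceive "must use condoms plus spermicidal agent during the study treatment period and for 8 weeks after the last dose of study drug". Permanently sterilized women are classed as not of childbearing potential.

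**Protocol Section 11.4.** "Sexually active males must use a condom during intercourse while taking the drug and for 8 weeks after stopping treatment". The condom rule extends to vasectomized men. Female partners are to be advised to use one of a hormonal method, an IUD/IUS or prior sterilization.

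Section 3.4 points to Appendix C only for the definition of childbearing potential. The SAP does not deal with contraception.

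**The concern.** The same patient can meet one passage and breach another. A woman who stops contraception in week 9 has met the Appendix C period but not the Section 3.4 period. A site that reads only one passage would counsel her by that passage, and a monitor would have no stated basis for classing her conduct as compliant or not.

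Embryo-fetal safety is at stake. Inclusion criterion 5 admits pre- and peri-menopausal women on tamoxifen, so women able to conceive are eligible. The protocol tests such women for pregnancy at baseline, every 2 cycles and at the end-of-treatment visit, and it lists pregnancy among its events of special interest. Appendix D places the end-of-treatment visit 30 days after treatment and schedules no pregnancy test after it. The weeks on which the passages disagree therefore fall after the last scheduled test.

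**Working it through.** The plan derives no figure here, so there is nothing to reproduce. The check is a unit conversion and a side-by-side reading.

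**Duration.** Inputs are 6 months (Section 3.4) and 8 weeks (Appendix C and Section 11.4). Taking a month as 30.44 days:
- 6 months = 6 × 30.44 / 7 = 26.1 weeks.
- 8 weeks = 56 / 30.44 = 1.84 months.
- Difference = 26.1 − 8 = 18.1 weeks, or 6 − 1.84 = 4.16 months.
- Ratio = 26.1 / 8 = about 3.3.

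**Do the rules address different people?** No. Section 3.4 covers all patients, so women of childbearing potential and any fertile men fall under both it and Appendix C.

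**Starting point.** Section 3.4 counts from the last dose of study drug, as does Appendix C for men. Appendix C for women, and Section 11.4, count from the stopping of treatment. Section 6 has patients who stop everolimus continue anti-estrogen therapy while they benefit, so the two dates can differ. Suppose that study drug means everolimus, that treatment means both drugs, and that anti-estrogen therapy runs d weeks longer. The women's gap is then 26.1 − (8 + d) = 18.1 − d weeks. It is 18.1 weeks at d = 0 and closes at d of about 18. Page headers name everolimus as the study drug, and Section 11.1.5 equates study treatment with everolimus for adverse event reporting. Both favor d = 0, but Appendix C does not say so.

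**Methods.**

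| Situation | Section 3.4 | Appendix C | Section 11.4 |
|---|---|---|---|
| Woman of childbearing potential, barrier only | Meets | Does not meet | Not addressed |
| Tubal ligation at least six weeks before entry, no barrier | Does not meet | Meets | Not addressed |
| Sterilized male partner, no barrier | Does not meet | Meets | Not addressed |
| IUD/IUS plus barrier | Meets | Meets | Not addressed |
| Abstinence | Meets | Meets, if it is the usual way of life | Not addressed |
| Permanently sterilized woman | Bound by the rule | Outside the rule | Not addressed |
| Vasectomized man, no condom | Does not meet | Rule covers fertile men only | Does not meet |
| Female partner using a hormonal method | Not addressed | Not among the listed methods | Accepted |

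Rows 1 to 3 run in both directions, so neither Section 3.4 nor Appendix C is simply the stricter text. Adopting the longer period would not by itself remove the conflict.

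**The case against.** The strongest reply is that both periods are minimums. Appendix C tells nobody to stop at 8 weeks, and a patient who continues for 6 months from a common start also meets the 8-week period. That is right. A reader might infer that the passages give opposite instructions, but they do not: they set different minimums, and the risk is that a site reads only the shorter one. The reply does not reach the methods, where meeting one text can mean failing the other.

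Other limits also stand:
- **Section 11.4 covers men only.** For women, the contradiction rests on Section 3.4 against Appendix C. Inclusion criterion 5 is worded for women and no criterion names men as eligible, so the male provisions may apply to few or no patients.
- **The methods overlap in part.** Abstinence and an IUD/IUS plus a barrier can satisfy both texts. The hormonal difference is the weakest, because Appendix C's list is written for women in the trial and not for partners.
- **The consent form was not available.** A reader might infer that patients are being given conflicting consent information. The form may state a single rule, so only a risk can be claimed.

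**Conclusion.** Wrong as written: an internal inconsistency that should be corrected. Section 3.4 and Appendix C give different minimum periods to overlapping groups, their methods conflict in both directions, and no passage sets precedence.

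The gap of about 18 weeks (4.2 months) assumes a common starting date. Between Section 3.4 and Appendix C for fertile men the wording shares that date; for women it does not.

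It is tempting to say that 6 months against 8 weeks applies to every patient able to conceive or father a child, and to no one else. The documents do not support that scope. Section 3.4 binds all patients, so for permanently sterilized or post-menopausal women the contrast is 6 months against no Appendix C requirement. The number of women able to conceive cannot be estimated, because the plan gives no expected number of pre- or peri-menopausal patients.

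No statistical quantity depends on this point: sample size, power and the PFS analysis are unaffected.

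**What to change.** The sponsor should reconcile Section 3.4, Section 11.4 and Appendix C so that they state:
- one duration after treatment;
- one starting point, naming the drug whose last dose starts the period;
- one list of accepted methods for each population: women of childbearing potential, permanently sterilized and post-menopausal women, male patients if eligible (vasectomized men included), and female partners.

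Stating the rule once and cross-referring to it elsewhere would prevent a recurrence. The consent form should be checked against the reconciled text. Which duration and methods are right is a clinical decision for the sponsor, and this review does not propose one.

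The cost is an amendment to protocol wording and, if the consent form differs, to that form. No analysis, sample size or data collection changes.

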4. STUDY REGISTRATION

The patient must willingly consent after being informed of the procedures to be followed, the experimental nature of the treatment, potential benefits, alternatives, side-effects, risks and discomforts. Institutional Review Board (IRB) approval of this protocol and consent form is required. Eligible patients who wish to participate in the study will be enrolled into the study.

Registration must occur prior to the initiation of protocol therapy. Patients eligible to participate in the study may be enrolled through the SCRI Development Innovations, LLC (SCRI Innovations) Central Enrollment Desk. Registration may be done via email ([contact]) or [contact] or [contact]). Patient registration will be confirmed via email within 24 hours, or by the next business day.

5. STUDY DESIGN

This is a multi-centered, open-labeled, Phase II study in MBC. The patient population includes locally recurrent or MBC patients with cytologically or histologically confirmed hormone receptor-positive breast cancer who have demonstrated disease progression on prior anti-estrogen therapy or therapies. Eligible patients must have evaluable or measurable disease per RECIST v1.1.

CONFIDENTIAL

STUDY DRUG(S): EVEROLIMUS
FINAL PROTOCOL DATE: 19 JUNE 2014

SCRI INNOVATIONS STUDY NUMBER: BRE 212
VERSION 1.0

Everolimus will be administered at a dose of 10 mg PO daily combined with the last anti-estrogen therapy (tamoxifen, fulvestrant, anastrozole, letrozole, exemestane, toremifene, or LHRH agonists in conjunction with anti-estrogen therapy) to which they demonstrated disease progression. Anti-estrogen therapy will be administered at the US Food and Drug Administration (FDA) prescribed doses.

A treatment cycle will be defined as 4 weeks, with radiological evaluations every 2 cycles. Patients will be treated until disease progression, toxicity or intercurrent illness requiring cessation of treatment, withdrawal of consent, or other reasons outlined in Section 3.3.

The primary objective of this study is to determine efficacy as measured by progression-free survival. This study will be conducted by approximately 9 participating sites. A total of 46 patients will be enrolled.

CONFIDENTIAL

STUDY DRUG(S): EVEROLIMUS
FINAL PROTOCOL DATE: 19 JUNE 2014

SCRI INNOVATIONS STUDY NUMBER: BRE 212
VERSION 1.0

Figure 1

Study Schema

PHASE II N = 46

Everolimus 10mg PO once daily

Anti-estrogen Therapy

Treatment cycle = 4 weeks

Restaging: every 2 cycles

Patients will continue on treatment until disease progression, intolerance to side effects or withdrawal of consent.

5.1 Treatment Plan

5.1.1 Everolimus

Patients entering this study will receive everolimus in combination with the last anti-estrogen therapy on which they experienced disease progression at the FDA prescribed dose.

Everolimus 10 mg PO continuous daily dosing

Medication labels will comply with US legal requirement and be printed in English. They will supply no information about the patient. The storage conditions for everolimus will be described on the medication label.

The extent of absorption of everolimus through topical exposure is not known. Therefore, caregivers are advised to avoid contact with suspensions of everolimus tablets. Wash hands thoroughly before and after preparation of either suspension.

Everolimus is supplied by Novartis. Everolimus is formulated as tablets for oral administration of 1mg, 2.5mg, 5mg, and 10mg strength. Tablets are blister-packed under aluminum foil, which should be opened only at the time of administration as drug is both hygroscopic and light-sensitive. Refer to label for expiration date and storage conditions.

Everolimus will be self-administered (by the patient). Everolimus will be administered as two 5mg tablets on a continuous daily dosing schedule. Everolimus should be taken at the same time every day either consistently with food or without food. Everolimus tablets should be swallowed whole with a glass of water. Patients should not chew or crush them. For patients unable to swallow tablets, everolimus tablet(s) should be dispersed completely in a 1 oz glass of water by gently stirring until the tablet(s) is fully disintegrated (approximately 7 minutes), immediately prior to drinking. The glass should be rinsed with 1 oz of water and the rinse should be completely swallowed to ensure that the entire dose is administered. Grapefruit juice should be avoided.

If vomiting occurs, no attempt should be made to replace the vomited dose.

If the patient forgets to take his dose before 6:00 pm, then the dose should be withheld that day and the everolimus should be restarted the following day.

CONFIDENTIAL

STUDY DRUG(S): EVEROLIMUS
FINAL PROTOCOL DATE: 19 JUNE 2014

SCRI INNOVATIONS STUDY NUMBER: BRE 212
VERSION 1.0

Everolimus drug compliance will be reviewed on Day 1 of each cycle. The research staff will document the amount of everolimus taken and missed by the patient.

Anti-estrogen Therapy (tamoxifen, fulvestrant, anastrozole, letrozole, exemestane, toremifene, or LHRH agonist in conjunction with anti-estrogen therapy)

The patient will be prescribed the last anti-estrogen therapy to which they demonstrated disease progression. Anti-estrogen therapy (tamoxifen, fulvestrant, anastrozole, letrozole, exemestane, toremifene, or LHRH agonist in conjunction with anti-estrogen therapy) will be administered according to the directions in the FDA approved labeling. Consult the appropriate package insert for specific information and instructions.

Restaging

A treatment cycle will be defined as 4 weeks, with radiological evaluations every 2 cycles (8 weeks). Patients will be evaluated for response to treatment before every odd numbered cycle with imaging and chemistry. Patients will be treated until disease progression, toxicity requiring cessation of treatment or withdrawal of consent.

5.2 Correlative Studies

Archival tumor tissue blocks, if available, will be collected and assayed for selected biomarkers. Details regarding sample submission will be provided in a separate lab manual.

5.3 VeriStrat® Assay

Serum samples will be collected from all patients at baseline and subsequent selected time points, for performing the VeriStrat assay. Treatment options for this study will not be based on the results of this testing. For details regarding the assay and sample collection, refer to Section 7.3.4 and Appendix F.

5.4 Concomitant Medications

Patients may receive full supportive care, including transfusion of blood products, anti-emetics, antimicrobials, etc., when appropriate, per institutional or ASCO guidelines, at the discretion of investigator. Bisphosphonates and RANK ligand inhibitors like XGEVA will be allowed for treating osteoporosis or bone metastases.

All concomitant medications and other significant drug therapies taken ≤ 30 days prior to start of study treatment and after start of study treatment, including blood transfusions, should be recorded.

Patients should be instructed not to take any additional medications (including over-the-counter products) during the course of the study without prior consultation with the investigator.

Antineoplastic Therapies

Treatment with systemic anticancer agents (chemotherapy, hormone therapy, targeted or biologic agents) other than the protocol treatment is not permitted until disease progression is documented per RECIST v1.1. Palliative radiotherapy or surgery may be allowed and should be discussed with the Study Chair prior to administration.

CONFIDENTIAL

STUDY DRUG(S): EVEROLIMUS
FINAL PROTOCOL DATE: 19 JUNE 2014

SCRI INNOVATIONS STUDY NUMBER: BRE 212
VERSION 1.0

Vaccinations

The use of live vaccines and close contact with those who have received live vaccines should be avoided one week before and during treatment with everolimus. Examples of live vaccines include intranasal influenza, measles, mumps, rubella, oral polio, BCG, yellow fever, varicella and TY21a typhoid vaccines.

5.5 CYP3A4 and/or PgP Inhibitors/Inducers/Substrates

Everolimus is metabolized by CYP3A4 in the liver and to some extent in the intestinal wall. Therefore, the following are recommended:

- Co-administration with strong inhibitors of CYP3A4 (e.g., ketoconazole, itraconazole, ritonavir) or P-glycoprotein (PgP) inhibitor should be avoided.
- Co-administration with moderate CYP3A4 inhibitors (e.g. erythromycin, fluconazole) or PgP inhibitors should be used with caution. If a patient requires co-administration of moderate CYP3A4 inhibitors or PgP inhibitors, reduce the dose of everolimus by approximately 50%. Additional dose reductions to every other day may be required to manage toxicities. If the inhibitor is discontinued, the everolimus dose should be returned to the dose used prior to initiation of the moderate CYP3A4/PgP inhibitor after a washout period of 2 to 3 days.
- Grapefruit or citrus juices affect P450 and PgP activity; therefore, concomitant use should be avoided.
- If patients require co-administration of a strong CYP3A4 inducer, consider doubling the daily dose of everolimus (based on pharmacokinetic data), using increments of 5 mg or less. This dose of everolimus is predicted to adjust the AUC to the range observed without inducers. However, there are no clinical data with this dose adjustment in patients receiving strong CYP3A4 inducers. If the strong inducer is discontinued, consider a washout period of at least 3 to 5 days (reasonable time for significant enzyme de-induction), before the everolimus dose is returned to the dose used prior to initiation of the strong CYP3A4 inducer.
- This dose adjustment of everolimus is intended to achieve similar AUC to the range observed without inducers. However, there are no clinical data with this dose adjustment in patients receiving strong CYP3A4 inducers. If the strong inducer is discontinued the everolimus dose should be returned to the dose used prior to initiation of the strong CYP3A4/PgP inducer.
- Oral contraceptives in preclinical and clinical data have shown everolimus to have CYP3A4 inhibitory activity rather than induction activity; induction of metabolism of contraceptive hormones by everolimus is unlikely. Consequently, administration of everolimus should not reduce the efficacy of oral contraceptives.

Refer to the listing of relevant inducers and inhibitors of CYP3A4 and the list of relevant substrates, inducers and inhibitors of PgP in Appendix E.

Everolimus and drugs influencing CYP3A4 enzyme

Everolimus is a substrate of CYP3A4, and a substrate and moderate inhibitor of the multidrug efflux pump, PgP (PgP, MDR1, and ABCB1). Therefore, extent of absorption and subsequent elimination of systemically absorbed everolimus may be influenced by products that are

CONFIDENTIAL

STUDY DRUG(S): EVEROLIMUS
FINAL PROTOCOL DATE: 19 JUNE 2014

SCRI INNOVATIONS STUDY NUMBER: BRE 212
VERSION 1.0

substrates, inhibitors, or inducers of CYP3A4 and/or PgP. Concurrent treatment with strong CYP3A4-inhibitors should be avoided. Refer to Appendix E for a comprehensive list of inducers and inhibitors of CYP3A4 and for a list of relevant substrates, inducers and inhibitors of PgP. Inhibitors of PgP may decrease the efflux of everolimus from brain or tumor and therefore increase everolimus concentrations in these tissues. In vitro studies showed that everolimus is a competitive inhibitor of CYP3A4 and of CYP2D6, potentially increasing the concentrations of products eliminated by these enzymes. Thus, caution should be exercised when co-administering everolimus with CYP3A4 and CYP2D6 substrates with a narrow therapeutic index. Clinical studies have been conducted in healthy subjects to assess pharmacokinetic drug interactions between everolimus and potential CYP3A modifiers (ketoconazole, verapamil, erythromycin, rifampin, midazolam, and HMGCoA reductase inhibitors (statins).

